1.3.2 Benefits

Benefits of furosemide in the HD population remain unproven at this time. Hypothesized benefits of furosemide therapy include improved volume status, BP control, and a decrease in volume-related symptoms during dialysis.

2 STUDY OBJECTIVE

The overall objective of this study is to test whether oral furosemide is safe and effective at increasing urine volume in HD patients.

2.1 Primary Objectives

Period 1 (dose escalation = short-term outcomes; 6-weeks) and Period 2 (follow-up = longer-term outcomes; 12-weeks)

Short-term and longer-term efficacy: To test the hypothesis that furosemide will increase 24-hour urine volume at its maximally tolerated dose in individuals with HD-dependent ESKD. 24-hour urine volumes will be used as the primary endpoint for both short-term and longer-term efficacy assessments.

Short-term and longer-term safety: To evaluate the short-term (6-weeks) and longer-term (12-weeks) safety of escalating doses of furosemide in individuals with HD-dependent ESKD. Safety outcomes will include the following:

- Serum potassium level <3.2 mEq/L
- Serum magnesium level <0.8 mg/dL
- Serum corrected calcium level <7 mg/dL
- Serum furosemide level >12 microgram/L
- Serious dialysis-associated hypotension defined as hypotension requiring hospitalization or treatment in an emergency room and not attributable to overt sepsis, acute myocardial infarction, or other cardiovascular event (e.g. aortic dissection)
- Severe or very severe rash, tinnitus, or hearing change not attributable to causes other than furosemide
- Inner EAR score decrease by ≥10 points

Short-term and longer-term tolerability: To evaluate the short-term and longer-term tolerability of furosemide in individuals with HD-dependent ESKD. Tolerability will be assessed by:

• Severe or very severe cramping, dizziness/pre-syncope, unusual tiredness/weakness, chest pain, nausea, vomiting, or diarrhea not attributable to causes other than furosemide

Short-term and longer-term acceptability: To evaluate the short-term and longer-term acceptability of furosemide in individuals with HD-dependent ESKD. Acceptability will be assessed by:

- Participant affirmative response to question: "If recommended, would you be willing to stay on the dose of furosemide you have received during the last week?"
- Recruitment rates
- Drop-out rates

Short-term adherence: To evaluate short-term and longer-term adherence to furosemide among individuals with HDdependent ESKD. Adherence will be assessed by:

- Pill counts
- Serum and urine furosemide levels

2.2 Exploratory Objectives

Period 1 (dose escalation = short-term outcomes) and Period 2 (follow-up = longer-term outcomes)

Short-term and longer-term clinical outcomes: Exploratory objectives are designed to expand understanding of the effect of furosemide on clinical outcomes in HD-dependent ESKD. We will analyze the following:

- 24-hour creatinine clearance
- 24-hour fractional excretion of urea
- 24-hour fractional excretion of sodium
- Pre-HD systolic BP
- Intradialytic hypotension (systolic BP <80 mmHg)²¹
- Intradialytic hypotension (systolic BP <90 mmHg)⁴¹
- IDWG
- UF volume
- UF rate
- Target weight achievement
- Post-HD weight-target weight difference
- Extra HD treatments
- Hospitalizations

[figure not shown]
3 INVESTIGATIONAL PLAN

[figure not shown]
3.1 Study Design (Figure 1)

[figure not shown]
This is a single center (multi-clinic), open-label, non-randomized pilot study to test whether oral furosemide is safe and effective at increasing urine volume in HD patients. The study will consist of 2 periods: a 6-week dose escalation period (period 1) and a subsequent 12-week follow-up period (period 2). During period 1, all participants will receive escalating doses of furosemide as tolerated, and we will examine the short-term safety and efficacy of furosemide. During period 2, all participants will continue the maximally tolerated period 1 furosemide dose, and we will examine the acceptability of and adherence to furosemide and the longer-term safety and efficacy of furosemide. The study duration is 18 weeks.

Figure 1. Study design.

Panel A. Study overview including both study periods (dose escalation and follow-up).

3.2 Allocation to Treatment Groups and Blinding

All participants will receive oral furosemide. Participants and investigators are unblinded.

3.3 Study Duration, Enrollment and Number of Participants

The study duration is 18 weeks and consists of a 6-week dose escalation period (period 1) and a subsequent 12week follow-up period (period 2). Our goal sample size is 36 participants in period 1 with the goal of >30 participants continuing on to period 2. We will recruit up to 40 participants to account for dropout and will recruit additional participants if fewer than 30 participants are eligible for period 2.

All participants will be recruited from the University of North Carolina (UNC)-owned Siler City, Pittsboro, Sanford, Lee County, and Carrboro "Carolina Dialysis" HD clinics. We will screen individuals for eligibility if they selfreport, on average, at least 1-cup urine/day. We selected this threshold based on a recent DOPPS analysis showing an association between self-reported urine volume of ≥1 cup/day and lower interdialytic weight gain (IDWG) and mortality.⁴² Our selection criteria exclude patients unlikely to respond to diuretics (i.e. minimal urine output), patients at increased risk for furosemide side effects (e.g. cirrhosis, electrolyte abnormalities, and concurrent use of interacting medications or substances), and patients likely to have urine output decline during the study (i.e. within the first 60-days of HD therapy). We will recruit patients 1:3, incident (60-180 days on HD): prevalent (>180 days on HD) to ensure study of both populations while accounting for the challenge of recruiting incident patients (e.g. fewer eligible patients, research reticence early in therapy). See **Section 3.4** for participant inclusion and exclusion criteria and **Section 9** for enrollment practices.

3.4 Study Population

Participant Inclusion Criteria

- Patient self-report of at least 1 cup urine/24-hours⁴²
- Age ≥18 years
- Receipt of thrice weekly in-center HD at a participating clinic (UNC-associated Carolina Dialysis- Carrboro, Siler City, Pittsboro, Sanford, and Lee County)
- ≥60 days receiving in-center HD
- Willingness to take study medication and undergo study testing
- Ability to provide informed consent

Participant Exclusion Criteria

- Known allergy to loop diuretic
- History of poor adherence to HD or medical regimen per nephrologist
- >1 hospitalization in prior 30-days
- Frequent hypotension (systolic BP <80 mmHg at >30% of HD treatments in prior 30-days)²¹
- Cirrhosis per nephrologist
- Hearing disorder per nephrologist
- Serum potassium <3.5 mEq/L, magnesium <1 mg/dL, or corrected calcium <8 mg/dL in prior 30-days
- Taking a non-loop diuretic (e.g. spironolactone, eplerenone, ethacrynic acid, thiazides)
- Taking an aminoglycoside, cisplatin, methotrexate, cyclosporine, ACTH, lithium, phenytoin, or oral/intravenous steroid
- Natural licorice consumption
- Prisoners, patients with significant mental illness
- Pregnant patients and nursing mothers

3.5 Study Drug/ Intervention

3.5.1 Description

Furosemide, the study drug, will be administered as tablets containing 20 mg, 40 mg or 80 mg furosemide.

During the 12-week follow-up period (period 2), participants who tolerated and accepted furosemide in period 1 will continue their maximally tolerated period 1 furosemide dose during the 12-weeks of follow-up. If a participant has electrolyte abnormalities or other side effects attributable to furosemide in period 2 (i.e. on their period 1 maximally tolerated dose), the dose will be lowered sequentially (i.e. dose de-escalation: $160 \rightarrow 120 \rightarrow 80$ mg twice daily, or, if on alternative dosing due to prior diuretic use, decrease dose by 50%, rounded to the nearest whole tablet strength of existing (i.e. available) furosemide tablet formulations, until tolerated). If side effects persist or if the participant chooses, oral furosemide will be stopped.

3.5.3 Preparation and administration of study drug

The study drug, furosemide, will be provided by the UNC Investigational Drug Service (IDS) which will be the Central Pharmacy for the study. Study drug kits will contain 2-week supplies during the dose escalation period (period 1) and 4-week supplies during the follow-up period (period 2). The PI will request the next supply of furosemide from IDS at each 2-week interval. Unless there is a contraindication (e.g. hypokalemia, serious hypotension), the investigator will escalate the furosemide dosing as described in *Sections 1.2 and 3.5.2*. If up-titration is contraindicated, the PI will notify IDS. If down-titration or discontinuation is indicated, the PI will notify IDS. At the end of period 1, participants will be provided with a 4-week supply of furosemide at the indicated dose (week 6). At the week 10 and 14 visits, additional 4-week supplies of furosemide at the indicated dose will be provided.

If the dose escalation schedule is interrupted (e.g., if a participant is hospitalized at the scheduled time of dose escalation and did not take study drug during the hospitalization), dose escalation will be delayed until the participant has had access to the current dose of study drug for a total of two weeks. If, due to considerable delays in dose escalation, a participant has not reached the final dose assignment by their Week 8 visit, the participant will remain at the current dose of study drug for the remainder of the study and the follow-up period (i.e., the 12-week post-escalation period) will be shortened accordingly such that the total duration of study participation is not increased as a result of the delay. For example, if dose escalation is not completed until week 8, the treatment phase will be 10 weeks rather than 12 weeks.

3.5.4 Participant adherence monitoring

Study drug containers will be returned to study coordinators at the conclusion of each 2-week period during dose escalation (weeks 2, 4 and 6), and at the conclusion of each 4-week period during follow-up (weeks 10, 14 and 18). Pill counts will be performed to assess participant adherence with prescribed study drug.

3.5.5 Concomitant therapy

Medication use (both oral and intravenous) will be collected at baseline and throughout the course of the study. Nonloop diuretic (e.g. spironolactone, eplerenone, ethacrynic acid, thiazides), aminoglycoside, cisplatin, methotrexate, cyclosporine, ACTH, lithium, phenytoin, and oral/intravenous steroid use are exclusion criteria. If these medications are initiated during follow-up the treating clinician will be contacted by the research team. If the prohibited drug cannot be discontinued, study medication will be withdrawn, and participants will continue to be followed.

3.5.6 Packaging

Furosemide will be distributed in patient-specific containers with the specified number of tablets (based on dosing listed in *Sections 1.2 and 3.5.2*) for every 2-week period during the dose escalation period (period 1) and the specified number

of tablets (based on dosing listed in *Sections 1.2 and 3.5.2*) for every 4-week period during the follow-up period (period 2). Labeling will include patient name, patient ID, protocol number, expiration date, and prescribing physician (PI).

3.5.7 Blinding of study drug

None

3.5.8 Receiving, storing, dispensing and returning study drug

The UNC IDS will maintain detailed records regarding furosemide dispensing, general study product accountability and patient specific study product accountability. Documentation includes study product storage, dispensing and final disposition.

3.5.9 Study drug storage

Furosemide will be stored at 25°C at the central UNC IDS pharmacy.

3.5.10 Dispensing study drug

The UNC IDS pharmacist or trained site designee will dispense the study drug to the study coordinator and complete a dispending/accountability log. Furosemide will be dispensed in well-closed, light-resistant containers. A study coordinator will dispense the study drug to the participant at the dialysis clinic at the below-described study visits and complete a dispensing/accountability log. The study coordinators will have appropriate training for dispensing and reconciling the study drug, and documentation of this training will be maintained in the study's regulatory binder.

3.5.11 Return or destruction of study drug

Study drug containers will be returned by participants at the end of each 2-week (dose escalation, period 1) and 4-week (follow-up, period 2) and remaining pills will be counted to assess adherence. Unused supplies of study drug will be returned to IDS once the pill count is completed and documented. In the event that a participant does not return study drug containers he/she will be instructed to stop taking any study drug from the non-returned container.

3.5.12 Participant access to study drug at study closure

Participants will have access to furosemide at study closure if deemed appropriate by their treating nephrologists.

4 STUDY PROCEDURES

4.1 Overview (Tables 2 and 3)

All study visits will occur at the participant's dialysis clinic at routinely scheduled HD treatments.

- There will be one study visit during the baseline period.
- Dose escalation period (period 1): Blood samples will be collected weekly at mid-week treatment visits (i.e. Wednesday or Thursday during weeks -1, 1, 2, 3, 4, 5 and 6) prior to scheduled dose initiation or dose titration. Urine samples will be collected twice during the dose escalation period at mid-week treatment visits (i.e. Wednesday or Thursday during weeks -1 and 5). Study drug visits will be conducted every two weeks at the first weekly treatment (i.e. Monday or Tuesday during weeks 0, 2, 4, and 6). This structure was selected so that blood results will be collected and analyzed the week prior to study drug dose titration. As such, test results will be available prior to potential dose titration. Adherence and symptom assessment visits will be conducted weekly at the first treatment of each week (i.e. Monday or Tuesday during weeks 1, 2, 3, 4, 5 and 6). Hearing

assessments will be conducted every two weeks at the first weekly treatment (i.e. Monday or Tuesday during weeks 2, 4, and 6).

- Follow-up period (period 2): Blood samples will be collected at mid-week treatment visits every 4 weeks (i.e. Wednesday or Thursday during weeks 9, 13 and 17). Study drug visits will be conducted at the first treatment of each of the subsequent weeks (i.e. Monday or Tuesday during weeks 10 and 14). As in the dose escalation period, this structure was selected so that blood results will be available prior to additional study drug administration. Study adherence and symptom assessment visits will be conducted every 2 weeks at the first weekly HD treatment in the scheduled week (i.e. Monday or Tuesday during weeks 8, 10, 12, 14, 16, and 18). Hearing assessments will be conducted every four weeks at the first weekly treatment (i.e. Monday or Tuesday during weeks 10, 14, and 18). Urine sample visits will be conducted at the mid-week treatments of the 12th week and final week of the follow-up period (i.e. Wednesday or Thursday during weeks 12 and 18). All remaining study drug will be returned at the first weekly treatment (i.e. Monday or Tuesday) of week 19. A final pill count (adherence assessment) will be performed upon study drug return (week 19).
- All HD treatments occurring during the 18-week study period will be considered study treatments, and all associated clinical data (BP, pre-HD and post-HD weights and dialysis treatment data such as UF volume, UF rate and dialysate composition) will be collected from the electronic health record (EHR).

Table 2. Study visits by	y type.								
Procedures	Baseline clinical assessment (Prior to study start, weeks -4 to -2)	Baseline electrolyte, urine, symptom, and hearing assessment (week -1)	Study drug visit (weeks 0, 2, 4, 6, 10, 14,)	Follow-up blood sample (weeks 1, 2, 3, 4, 5, 6, 9, 13, 17)	Follow-up urine sample (weeks -1, 5, 12, and 18)	Adherence and symptom assessment (weeks 1, 2, 3, 4, 5, 6, 8, 10, 12, 14, 16, and 18)	Hearing assessment (weeks 2, 4, 6, 10, 14, and 18 weeks)	Clinical data collected at every HD treatment during study period (weeks -4 to 18)	Study drug return (week 19)
Complete medical history	х								
Pregnancy status inquiry	Х								
Serum electrolytes and furosemide level		х		х					
24-hour urine		Х			Х				
Symptom assessment		Х				Х			
Hearing assessment		Х					х		
Study drug administration			Х						
Patient acceptance assessment									
Drop-out rates	Х							х	
Pill counts						Х			Х
End of trial study drug return									Х
BP monitoring	Х							х	
Weight monitoring	Х							х	
UF volume/rate	Х							Х	
Extra HD treatments	Х							х	
Hospitalizations	Х							х	

Table 2. Stud	Table 2. Study visits by week.																					
Week(s)	-4 to -2	-1	0	1	2	3	4	5	6	7	8	9	10	11	12	13	14	15	16	17	18	19
Procedures																						
Complete	Х																					

medical history																						
Pregnancy status inquiry	Х																					
Serum electrolytes and furosemide level		x		x	x	x	x	x	х			x				x				x		
24-hour urine		Х						Х							Х						Х	
Symptom assessment		х		х	х	х	х	х	х		х		х		х		х		х		х	
Hearing assessment		х			х		х		х				х				х				х	
Study drug administration			х		х		х		х				х				х					
Patient acceptance assessment				х	х	х	х	х	х		х		х		х		х		х		х	
Drop-out rates	Х	Х	Х	Х	Х	Х	Х	Х	Х	Х	Х	Х	Х	Х	Х	Х	Х	Х	Х	Х	Х	
Pill counts				Х	Х	Х	Х	Х	Х		Х		Х		Х		Х		Х		Х	Х
Study drug return																						Х
BP monitoring	х	x	x	х	х	х	х	х	х	х	х	х	х	х	х	х	х	х	х	х	х	
Weight monitoring	Х	х	х	х	х	х	х	х	Х	Х	х	х	х	х	х	Х	х	х	х	х	х	
UF volume/ rate	Х	Х	Х	Х	Х	Х	Х	Х	Х	Х	Х	Х	Х	Х	Х	Х	Х	Х	Х	Х	Х	
Extra HD treatments	Х	х	х	х	х	х	х	х	х	х	х	х	х	х	х	х	х	х	х	х	х	
Hospitalizations	Х	Х	Х	Х	Х	Х	Х	Х	Х	Х	Х	Х	Х	Х	Х	Х	Х	Х	Х	Х	Х	

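### The documents conflict on whether study drug is supplied in week 18; on the dispensing text, the final 24-hour efficacy urine falls after supply has run out

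*Combined protocol and SAP*

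**What the plan says.** On dispensing, section 3.5.3 gives two-week kits in period 1 and a four-week kit at week 6, and then: "At the week 10 and 14 visits, additional 4-week supplies of furosemide at the indicated dose will be provided". The period 2 text of 4.1 and the detailed weeks 10 and 14 paragraph of 4.3 agree. The by-type schedule table has the column "Study drug visit (weeks 0, 2, 4, 6, 10, 14", and the by-week table leaves week 18 blank for drug administration. The opening paragraph of 4.3 differs: it lists study drug administration visits at weeks 10, 14 and 18, with no quantity for week 18.

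On return, section 3.5.4 has containers come back "at the conclusion of each 4-week period during follow-up (weeks 10, 14 and 18"), and 3.5.11 also ties return to the end of each kit period. Section 4.1 says "All remaining study drug will be returned at the first weekly treatment (i.e. Monday or Tuesday) of week 19", followed by a final pill count. The tables and 4.3 also put the return in week 19.

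On duration, section 3.5.2 says participants "will continue their maximally tolerated period 1 furosemide dose during the 12-weeks of follow-up", and 3.5.3 gives the example that "if dose escalation is not completed until week 8, the treatment phase will be 10 weeks rather than 12 weeks".

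On the final urine, section 4.1 states "Urine sample visits will be conducted at the mid-week treatments of the 12th week and final week of the follow-up period", which it identifies as weeks 12 and 18. Sections 4.1 (tables) and 4.4 also list week 18.

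**The concern.** The efficacy hypothesis in section 2.1 concerns urine volume while on the maximally tolerated dose. Period 2 has only two 24-hour collections, and section 6 says the longer-term endpoints are measured in that period. If supply ends before the second collection, drug status at that collection depends on missed doses, retained tablets and visit timing rather than on the assigned dose.

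This could understate the longer-term response. It could also look like loss of effect with duration in the section 6.3.4 models, which use time (dose) as the fixed effect. Section 6.2 uses urine furosemide, present or absent, as an adherence measure, so a participant who took every tablet could be recorded as absent. Section 4.4 does not list the time of the last dose among the data collected, so this could not be separated out afterwards.

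**Working it through.** **Conventions.** Day 0 is the first treatment of week 0. The first treatment of week w is day 7w and the mid-week treatment is day 7w + 2. Assumptions not in the documents: the collection runs from 08:00 on day 7w + 1 to 08:00 on day 7w + 2; doses are taken at about 08:00 and 20:00; kits hold exactly the stated number of weeks, since no overage is mentioned.

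**1. The plan's own figure.** Section 3.3 gives 18 weeks (6 + 12). The kits give 2 + 2 + 2 + 4 + 4 + 4 = 18 weeks, so the two agree. In days this is 3 × 14 + 3 × 28 = 126, that is days 0–125. The labelled weeks 0 to 18 are 19 weeks, or 19 × 7 = 133 days, so one labelled week has no kit.

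**2. Which week that is.** In its intolerance rules, section 4.3 treats the week 0 kit as the dose for weeks 0 and 1, and the week 4 kit as the dose for weeks 4 and 5. On that mapping the week 14 kit covers weeks 14–17, and its last day is 14 × 7 + 27 = 125.

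**3. Urine collections against supply.**

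| Urine | Collection days | Inside days 0–125? | Scheduled doses in the 24 h |
|---|---|---|---|
| Week 5 | 36–37 | yes | 2 |
| Week 12 | 85–86 | yes | 2 |
| Week 18 | 127–128 | no | 0 |
| Week 17 (if moved) | 120–121 | yes | 2 |

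**4. Gap before the week 18 collection.** If the last dose is at 20:00 on day 125, the gap to 08:00 on day 127 is 36 h. If dosing began on the evening of day 0, the last dose is at 08:00 on day 126 and the gap is 24 h. Section 1.2 gives a diuretic effect of 6 to 8 h. That is a general figure; persistence in hemodialysis patients is not given.

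**5. What would change drug status.** A 28-day kit holds 56 doses. Both doses on day 127 would be covered by 4 left-over doses (last dose on day 125) or 3 (last dose on day 126): 4/56 = 7.1% and 3/56 = 5.4%. Section 6.1 counts fewer than 20% of pills remaining as adherent, which allows up to 11/56 = 19.6%. The tablets must still be in hand, however. If the container is returned at the first treatment of week 18 (day 126), when section 4.1 schedules the adherence visit, they are gone before the collection. With the urine day nominal, a week 14 visit at least 2 days late (125 + 2 = 127) would also bring the collection inside supply; section 4.3 allows −4 to +4 days.

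**6. Do the duration statements settle it?** No. Twelve weeks fits weeks 6–17 and also weeks 7–18. Ten weeks fits weeks 8–17 and also weeks 9–18. Section 4.1 lists week 6 assessments under period 1 and calls week 18 the last follow-up week, so the later reading is open.

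**7. If drug is dispensed at week 18.** Even one week's supply would cover days 126–132, and the collection would be on drug.

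**The case against.** The strongest reply is that dosing through week 18 was planned and the dispensing lists are off by one week label. Section 4.3 opens with a week 18 drug administration visit, section 4.1 treats week 18 as part of follow-up, and a final return and pill count in week 19 fits a supply still in use. This is a fair reading and cannot be ruled out. It would be wrong to say that nothing in the documents points to dosing in week 18. A reader might also infer from the 12-week and 10-week statements that treatment must end at the start of week 18; step 6 shows that they fit either reading. The header of the by-type table ends in a stray comma and is weak evidence alone, but the by-week table and sections 3.5.3, 4.1 and 4.3 do not depend on it.

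It can also be said that the off-drug case is narrow: it needs full adherence, nominal days, no spare tablets and no week 18 kit. That is true. Relaxing those conditions, however, makes drug status vary with missed doses and visit timing, and with no last-dose time listed the variation would go unseen.

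Finally, the week 12 collection is unaffected, and no section says whether week 12, week 18 or both define the longer-term endpoint. That limits the damage but does not remove it.

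**Conclusion.** The conflict is real and should be fixed. If the dispensing text is followed, with no overage and nominal days, a fully adherent participant has 0 scheduled doses in the week 18 collection, against 2 at week 5 and 2 at week 12. The last supplied dose comes 24 to 36 h before the week 18 collection starts, on the assumed dose and collection times.

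A reader might infer that the final urine will be off drug for everyone, or that longer-term efficacy will be biased by a known amount. The documents support neither. Whether week 18 is supplied is exactly what they leave unsettled, and they give no figure from which to size the effect on response. If supply through week 18 was intended, the problem disappears once the text says so.

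**What to change.** - Reconcile sections 3.5.3, 3.5.4, 3.5.11, 4.1 (text and both tables) and 4.3 on supply and return, so that the final efficacy urine falls inside dispensed supply. The investigators should state which rule was intended.
- If no supply covers week 18, move only the final 24-hour urine to the mid-week treatment of week 17. Update 4.1 and its tables, 4.4, the early-withdrawal assessments in 4.5, and the remuneration timing in 9.1 that is tied to urine collections.
- In either case, record the date and time of the last dose at each urine collection.
- As a separate, minor item in the same edit, settle the follow-up blood weeks: 9, 13 and 17 in 4.1 and its tables, but 10, 14 and 18 in 4.4.

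**Cost.** A text correction and one added data field. If the urine is moved, the last efficacy reading comes one week earlier. If the blood weeks are settled as 10, 14 and 18, the moved urine would also lose its same-week serum, which affects only the exploratory clearance and fractional excretion measures.
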